1. SYNOPSIS

Name of Sponsor/Company: BioAegis Therapeutics Inc.	
Name of Investigational Product: Recombinant Human Plasma Gelsolin (rhu-pGSN)	
Name of Active Ingredient: rhu-pGSN	
Title of Study: A Phase 1b/2a, Double-blind, Placebo-controlled, Dose-escalation Study to Evaluate the Safety, Pharmacokinetics, and Pharmacodynamics of Recombinant Human Plasma gelsolin (rhu-pGSN) Added to Standard of Care in Subjects Hospitalized for Acute Community-acquired Pneumonia (CAP)	
Study center(s): 4-8 sites in Australia	
Studied period (years): Estimated date first subject enrolled: July 2018 Estimated date last subject completed: December 2018	Phase of development: 1b/2a
Objectives:	
Primary	

 To evaluate the safety and tolerability of single and multiple ascending doses of rhu-pGSN administered by once-daily intravenous (IV) push to hospitalized subjects with a primary admitting diagnosis of community-acquired pneumonia (CAP) To identify the maximum tolerated dose (MTD) or recommended Phase 2b/3 dose 	
Secondary	

 To characterize the pharmacokinetic (PK) profile of rhu-pGSN after single or multiple IV doses 	
Exploratory	

 To assess the quantitative relationship of pGSN levels at baseline with clinical outcomes, changes in prognostic indices and inflammatory biomarkers, and etiologic pathogen type To assess the relationship between rhu-pGSN dose and clinical response and changes in surrogate biomarkers of efficacy 	
Immunogenicity:	

 To investigate the post-treatment development of antibodies against rhu-pGSN by Day 28 	
Methodology:	
Each dosing cohort will include 8 subjects randomized 3:1 rhu-pGSN:placebo (6 rhu-pGSN subjects:2 placebo subjects).	
Dose will be based on actual body weight. Dose escalation will involve 3 dose levels of rhu-pGSN (6, 12, and 24 mg/kg) in patients admitted for CAP. Dose escalation will only occur after post-therapy safety information on all subjects in the prior cohort has been reviewed at Day 7 for the single-dose [SD] and multiple-ascending dose [MAD] arms).	

The MAD portion of the study will commence once single doses of 6 mg/kg of rhu-pGSN are shown to be acceptably safe. The first 2 doses must be administered in the hospital, but the third dose can be given in a monitored outpatient setting where appropriate.

Discharged subjects will return for follow-up 7 days after the initiation of therapy (Day 7) and on Day 28 for the End-of-Study Visit.

To assess safety and tolerability starting at the initiation of study therapy, subjects will undergo physical examinations (PE; including vital sign measurements), adverse event (AE) assessments, concomitant medication assessments, safety laboratory testing, and electrocardiograms (EKG) completed locally, and other testing as per local custom.

Once informed consent is obtained:

1. Randomize to enrolling treatment arm.
2. Perform PE and document radiographic evidence of pneumonia if not previously completed in preceding 36 hours; calculate Confusion, Urea >7 mmol/L, Respiratory rate ≥ 30 /min, Blood pressure systolic <90 or diastolic ≤ 60 , and age ≥ 65 years (CURB-65), Sequential Organ Failure Assessment (SOFA), and Pneumonia Severity Index (PSI) scores.
3. Obtain blood and sputum cultures, routine/standard labs, and EKG per standard of care (SOC) (if not already performed). The microbiology lab is encouraged to also perform sputum Gram-stains, antigen detection, immunoassay, and genomic diagnostic tests when available.
4. Draw blood for baseline pGSN levels, C-reactive protein (CRP), procalcitonin level, and 10 mL aliquot to be frozen for subsequent biomarker assays.

Screening laboratory and other tests can serve as baseline values for participants (no need to repeat lab tests at entry if done within the prior 36 hours unless dictated by SOC).

Obtain repeat chest x-rays (CXRs), computed tomography (CT) scans, and labs/cultures, etc. during the hospitalization if/when indicated by SOC.

Recalculate CURB-65 and Δ SOFA scores and redraw procalcitonin, pGSN, and biomarker samples on Day 3 or 4 and Day 7.

Doses in the multiple-dose arms should be given at 24-hour (\pm 60-minute) intervals. For the one dose in the SD arm and the first 2 doses in the multiple-dose arms, blood will be drawn within 30 minutes predose, and 5-10 minutes after the end of administration, as well as 2, 8, 12 and/or 16, and 24 hours after the end of administration (\pm 30 minutes) for analysis of plasma for maximum concentration (C_{max}), time to maximum concentration (T_{max}), terminal half-life ($T_{1/2}$), area under the curve from time zero to 8 hours (AUC_{0-8}), and area under the curve from time zero to infinity (AUC_{inf}). Sampling at both the 12- and 16-hour time points is encouraged where feasible, but only one of these two times is required. Identical PK sampling is encouraged on Day 3 where feasible, but not required in the multiple-dose arms. In the multiple-dose arms, the sample at 24 hours after the prior dose must be drawn before the next dose is given and can serve as the predose sample for the next dose as long as administered within the subsequent 30 minutes.

The syringe, filter, and extension tubing should be connected after disconnecting the IV as close to the patient as possible. On Day 28, collect samples for analysis of pGSN levels and antibodies against pGSN.

Number of subjects (enrolled):

A total of 32 (6 rhu-pGSN and 2 placebo recipients per dose cohort x 4 dosing levels)

Major inclusion criteria:

1. Age ≥ 18 years

2. Gender: either
3. Informed consent obtained from subject
4. Domicile: home, assisted living, rehabilitation facility, or nursing home (as long as the prospective participant is capable of providing written informed consent)
5. Duration of infection precipitating hospitalization by history <14 days
6. Planned or actual admission to hospital with a primary diagnosis of CAP within 24 hours of presentation to the hospital
7. Primary admitting diagnosis of pneumonia supported by a compatible clinical presentation with a documented infiltrate consistent with pneumonia on chest radiograph or CT, as assessed by the admitting emergency-department (ED), clinic, or ward physician or equivalent caregiver
 - Recommended (not mandatory) guidance/discretionary criteria defining patients with CAP:
 - At least 2 symptoms: difficulty breathing, cough, production of purulent sputum, chest pain
 - At least 2 vital sign abnormalities: fever, tachycardia, tachypnea
 - At least one finding of other clinical signs and laboratory abnormalities: hypoxemia, clinical evidence of pulmonary consolidation, an elevated total white blood cell (WBC) count or leukopenia
 - Chest imaging showing new (or presumed new or worsening) infiltrates
 - Receipt of antibiotic treatment prior to presentation does not exclude the patient

Major exclusion criteria:

1. Pregnant or lactating women
2. Intubation, vasopressor support, or admission to the intensive care unit (ICU) directly from the ED/office (fluids for responsive hypotension is not a reason for exclusion)
3. Use of any investigational drug in the past 30 days
4. Hospitalization during the last 30 days
5. Residence within the last 30 days in long-term care facility where the patient remains persistently unable to participate in the routine activities of daily living
6. Active underlying cancer treated with systemic chemotherapy or radiation therapy during the last 30 days
7. Known or suspected immunosuppressive disease or therapy (including steroid use equivalent to prednisone ≥ 20 mg/day for >7 days or known advanced human immunodeficiency virus (HIV) infection with CD4 count $\leq 200/\text{mm}^3$; specific testing for HIV status or CD4 count is not required but can be done at the discretion of the caregivers)
8. Active congestive heart failure, myocardial infarction, or pulmonary embolism; cardiopulmonary arrest in last 30 days
9. Weight >100 kg
10. Otherwise unsuitable for study participation in the opinion of the investigator

Investigational product, dosage and mode of administration:

Vials containing 200 mg of lyophilized rhu-pGSN will be reconstituted to a volume of 5 mL with 4.56 mL of sterile water and drawn up into suitably sized syringes as dictated by the dose.

- SD: single IV push at a rate between 5 and 20 mL/min through a standard 0.2-micron filter at 6 mg/kg
- MAD: once-daily IV push at a rate between 5 and 20 mL/min through a standard 0.2-micron filter for 3 days at 6 mg/kg, 12 mg/kg, or 24 mg/kg administered on 3 consecutive days approximately 24 hours (\pm 60 minutes) apart.

Duration of treatment:

1 day (SD) or 3 days (MAD)

Subject screening: within 24 hours of presentation to hospital; enrollment and initiation of study treatment begun within 36 hours of presentation.

Duration of subject participation:

28 days post-first dose

Reference therapy, dosage and mode of administration:

Placebo (dosed at a volume of 0.15, 0.30, or 0.60 mL/kg [depending on the dosing arm] up to 60 mL normal saline solution [NSS] via IV push [to match the volume of rhu-pGSN for a patient of that size in the specific dosing arm] injected at 5-20 mL/min through a standard 0.2-micron filter)

Endpoints/Outcomes:

Primary

- Incidence, causality, and severity of AEs and SAEs graded according to the National Cancer Institute (NCI) Common Terminology Criteria for Adverse Events (CTCAE) version 4.03 (or equivalent); clinically significant laboratory and/or EKG abnormalities; death irrespective of cause; cause of death per investigator, including relationship to study drug; use of vasopressors, intubation, or transfer to the ICU or equivalent through Day 7

Secondary

- PK for rhu-pGSN including, but not limited to: C_{max} , T_{max} , $T_{1/2}$, AUC_{0-8} , AUC_{inf} (levels measured within 30 minutes predose, 5-10 minutes after the end of administration, and 2, 8, 12 and/or 16, and 24 hours (\pm 30 minutes) after each dose (Day 3 sampling in multiple-dose arms is optional))
- Incidence, causality, and severity of AEs and serious adverse events (SAEs) graded according to the NCI CTCAE version 4.03 (or equivalent); clinically significant laboratory and/or EKG abnormalities as required by SOC; death irrespective of cause; cause of death per investigator, including relationship to study drug; use of vasopressors, intubation, or transfer to the ICU or equivalent through Day 28 (secondary time point)

Exploratory

- Baseline and sequential pGSN levels
- Clinical outcomes: 28-day survival; ICU days; days on ventilator or pressers; days on antibiotics; duration of hospitalization; Δ SOFA and CURB-65 scores
- Temporal profiles of inflammatory biomarkers
- Pathogen type (bacterial; viral; other; unknown) determined per customary work-up at each site

Immunogenicity

- Presence anti-rhu-pGSN antibodies at Day 28

Enrollment Procedure:

After informed consent, subjects with a primary diagnosis of CAP to be admitted to the medical wards will be screened for eligibility as soon as possible. Medical history, including concomitant medications and current clinical status, will be recorded.

- Pregnancy test (urine/blood) for women of childbearing potential
- A CXR and/or CT of the chest if not previously completed in preceding 36 hours
- If inclusion and exclusion criteria are satisfied, the subject will be enrolled and assigned to a baseline risk group CURB-65 ≤ 3 or >3 . Randomization will not be stratified by risk group. Screening labs can be used for baseline values. The day of admission will be used as baseline (Day 1) for analysis purposes. Subjects will receive rhu-pGSN or placebo at the assigned dose within 36 hours of presentation.

Subject Replacement

Only subjects missing doses or discontinuing at random (non-informative) before the primary visit on Day 7 will be replaced as originally randomized to receive rhu-pGSN or placebo. Safety data from all subjects treated with ≥ 1 dose will be collected. Subjects discontinuing the study after the Day-7 Visit will not be replaced.

Data and Safety Monitoring Board:

[name], Clinical Research Organization (CRO) monitor.

Statistical Methods and Sample Size Rationale for Power Calculations:

All subjects given ≥ 1 dose of study drug will be included in the intention-to-treat population; missing values will not be imputed but safety data (death and other AEs) will be carried forward. Subjects receiving all 3 doses and evaluable at Day 7 will constitute the per-protocol population. The expectation is that both populations will be almost identical.

Results will be summarized via summary statistics separately for each pGSN dose level in the SD and in the MAD portions of the trial, and for all placebo subjects pooled. No data will be excluded from the summary statistics and analyses, and missing data will not be imputed.

Demographics and disease-related characteristics will be summarized via counts and percentages of subjects for categorical variables, and by N, mean, median, standard deviation, minimum, maximum for continuous variables. Summaries will be performed separately by dose group and placebo subjects (all placebo subjects combined), and for all study subjects combined.

AE data will be summarized by counts and proportions of subjects having an AE, each AE type, and an AE of each System Organ Class. These summaries will be provided for each dose and placebo (all placebo subjects combined). SAEs will be summarized similarly. Reasons for any early discontinuations will be summarized similarly.

Biomarker, clinical outcome, and laboratory data will be summarized via counts and percentages of subjects for categorical variables, and by summary statistics (N, mean, median, standard deviation, minimum, maximum, 90% confidence intervals, etc.) for baseline, each observed time point, and change from baseline at each observed time point for continuous variables. Data will be assessed via graphical and Shapiro-Wilk statistic for closeness to normal distribution and if substantial departure is observed, transformation (e.g., natural log, reciprocal, square root, ranks) may be employed to derive the summary statistics. Details will be in the statistical analysis plan (SAP).

To complete the PK analyses, plasma specimens will be periodically sampled relative to study drug administration and stored frozen for pGSN measurements. For the 1 dose in the SD arm and the first 2 doses in the MAD arms, blood will be drawn for analysis of C_{max} , $T_{1/2}$, AUC_{0-8} , and AUC_{inf} . Identical PK sampling is encouraged on Day 3 where feasible (but not required) in the multiple-dose arms.

The immunogenicity will be assessed at the last visit on Day 28 ± 2 days. Antibodies against rhu-pGSN will be assayed from frozen specimens to determine whether the investigational product induces an antibody response in recipients.

The table below presents the Minimum Sample Size such that there is 90% probability of observing at least 1 AE of a certain type if the TRUE underlying AE rate.

Sample Size	TRUE underlying AE rate
6 (each pGSN dose level)	32%
8 (pooled placebo)	21%
24 (pooled pGSN)	10%

With each sample size presented in the table above, if zero AEs of a certain type are observed, one could be "90% confident" the TRUE underlying rate for that AE is at most the rate indicated above.

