4.4. Preclinical and Clinical Experience

4.4.1. Preclinical Experience

The preclinical studies of pGSN have revealed no safety concerns related to its mechanism of action or formulation. No functional effects on the respiratory system and no systemic toxicity attributed to rhu-pGSN or the formulation excipient, 0.1% polysorbate 80 (Tween-80), were observed in these studies at the highest achievable doses. No clinically relevant pathological effects were evident in rats or monkeys following administration of pGSN or 0.1% polysorbate 80 vehicle for up to 28 days by inhalation or for 14 days by intravenous (IV) injection.

Exposures to the lower respiratory tract of rats and monkeys in the repeat-inhalation dose toxicity studies were up to approximately 75 and 250 times, respectively, the estimated level at the proposed starting dose to be administered to patients with CAP. Based upon the lack of test article-related effects, safety margins are estimated to be in excess of 4.5 and 30 times (for rat and monkey, respectively) the highest planned clinical dose.

The pharmacokinetic (PK) profile of rhu-pGSN following inhalation, intratracheal, IV, or oral administration is consistent with that of a relatively stable, high molecular weight protein. Detectable systemic absorption of rhu-pGSN following inhalation exposure is not extensive. No changes in endogenous plasma gelsolin levels were detected using an enzyme-linked immunosorbent assay (ELISA) following aerosol administration of pGSN to monkeys at presented dose levels up to 9,550 mg/kg. The half-life of rhu-pGSN-related radioactivity in the lung was approximately 10 to 16 hours in normal rats and monkeys, respectively, following pulmonary exposure.

Test article-related effects observed following repeat aerosol administration of pGSN under conditions of continuous pulmonary exposure was limited to minimal microscopic changes in the lungs of monkeys. The microscopic change is attributed to an immunogenic response as evidenced by the detection of antibodies to rhu-pGSN. The antibodies appeared to be directed against the human-specific epitopes of intact rhu-pGSN and caused no clinical or pathological signs of serum sickness. Thus, the immunogenic reaction to rhu-pGSN in monkeys appears to be a species-specific response and, therefore, is not considered to be clinically relevant.

No cardiovascular effects were noted in monkeys receiving pGSN by either inhalation or IV administration.

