- ^a Collect sputum sample as soon as possible if not collected at the time of hospital admission. The microbiology lab is encouraged to also perform sputum Gram-stains, antigen detection, immunoassay, and genomic diagnostic tests when available. If fevers or chills are present, 2 sets of blood cultures are recommended at the discretion of the caregivers.
- ^b Record blood pressure, oral temperature, respiration rate, and heart rate, as well as pulse oximetry. To be measured during study drug administration at the following time points: predose, at the end of administration, and 30 minutes after the end of administration.
- ^c When EKGs are to be collected at the same time point as a blood collection, EKGs should be collected first. Three serial, resting, supine 12-lead EKGs are to be conducted within 10 minutes total time.
- ^d Blood for PK will be drawn within 30 minutes predose, 5-10 minutes after the end of administration, and 2, 8, 12 and/or 16, and 24 hrs (\pm 30 minutes) after the end of administration. Sampling at both the 12- and 16-hour time points is encouraged where feasible, but only one of these two times is required. The last PK sample (i.e., 24 hours after the end of administration) will occur on Day 2. Samples are spun and plasma frozen and sent to a central lab for analysis.
- ^e A 10-mL aliquot (equal parts serum and plasma) will be frozen for subsequent biomarker analysis including, but not limited to, procalcitonin, pGSN, TNF α , TGF β , IL1 β , IL1 α , IL2, IL4, IL6, IL10, IL17a levels and sent to a central lab for analysis.
- ^f Sample to be sent to a central lab for analysis.
- ^g Subjects are to be monitored for administration site reactions during study drug administration and for 1 hour after its completion.
- ^h Day 1 is the first day of study treatment. Baseline tests (including blood draws) should be performed prior to administration of the first dose.
- ⁱ Test/assessment does not have to be repeated if performed within the prior 36 hours unless dictated by standard of care.

Table 6: Schedule of Assessments: Multiple-Ascending Dose Phase

Visit	Screening	Baseline/ Randomization/ Pre-Treatment	Follow-up days					Early Termination/ End-of-Study Visit
			2	3	4	7 ± 1	14 ± 2	
Day	-1 to 0	1^j						28 ± 4
Informed consent	X							
Eligibility assessment	X							
Medical history/ signs and symptoms	X	X ^k						
Sputum culture ^a	X							
Blood or urine pregnancy	X (for women of childbearing potential only)							X

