## 9. PHARMACOKINETICS (PK)

All PK summary tables and figures will be based on the PK Population. All listings will be based on the Safety Population (Actual Treatment). All analyses will be done by treatment group.

For the 1 dose in the SD arm and the first 2 doses in the MAD arms, blood will be drawn within 30 minutes pre-dose, and 5-10 minutes after the end of administration, as well as 2, 8, 12 and/or 16, and 24 hours after the end of administration ( $\pm$  30 minutes) for analysis. Identical PK sampling is encouraged on Day 3 where feasible (but not required) in the multiple-dose arms.

In this section (section 9):

- The rhu-pGSN treatment group will be referred to the Active treatment group.
- Exogenous pGSN concentrations will be referred to as rhu-pGSN concentrations.
- Endogenous pGSN + Exogenous pGSN (total) will be referred to as pGSN

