#### **Day 1: SD/MAD & Day 2/3: MAD**

AUC 0-t	The area under the plasma concentration-time curve, from time 0 (time of dosing) to the last time point (24 hours) with measurable analyte concentration, calculated by the log down, linear up trapezoidal method.  AUC 0-t will additionally be calculated for the estimated rhu-pGSN profile for both the change from pre-dose on each study day and the double-delta method.
AUC 0-8	The area under the plasma concentration-time curve, from time 0 (time of dosing) to the 8 hours concentration, calculated by the log down, linear up trapezoidal method.  AUC 0-8 will additionally be calculated for the estimated rhu-pGSN profile for both the change from pre-dose on each study day and the double-delta method.
AUC 0-inf	The area under the plasma concentration-time curve from time 0 extrapolated to infinity. AUC 0-inf is calculated as the sum of AUC 0-t plus the ratio of the last measurable plasma concentration to the elimination rate constant ( $k_{el}$ ).
C max	Maximum observed concentration.  C max will additionally be calculated for the estimated rhu-pGSN profile for both the change from pre-dose on each study day and the double-delta method.
T max	Time to maximum observed drug concentration. If the maximum value occurs at more than one time point, T max is defined as the first time point with this value.

$k_{el}$	Apparent terminal elimination rate constant calculated by linear regression of the terminal linear portion of the log concentration vs. time curve.
$t_{1/2}$	Apparent elimination half-life, calculated as $\ln(2)/k_{el}$
%AUC ext	Percentage of the extrapolated area under the plasma concentration-time curve, calculated as $100\% * [AUC_{0-inf} - AUC_{0-t}] / AUC_{0-inf}$
$C_L/F$	Apparent clearance calculated as $Dose/AUC_{0-inf}$ .
$V_z/F$	Apparent volume of distribution at the terminal phase, calculated as $Dose / (k_{el} \times AUC_{0-inf})$ .
DN_C max	Dose-normalized C max , calculated as C max divided by dose DN_C max will additionally be calculated for the estimated rhu-pGSN profile for both the change from pre-dose day 1 and the double-delta method..
DN_AUC 0-inf	Dose-normalized AUC 0-inf , calculated as AUC 0-inf divided by dose

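### Half-life and AUCinf of rhu-pGSN are derived from total pGSN over 24 hours, so they mix drug with endogenous protein and may rest largely on extrapolation

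*Protocol*

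**What the plan says.** Protocol 5.2.2 names T1/2 and AUCinf among the secondary PK endpoints for rhu-pGSN. Samples are taken before the dose, 5-10 minutes after the end of administration, "as well as 2, 8, 12 and/or 16, and 24 hours after the end of administration"; only one of the 12 h and 16 h samples is required. For the single-dose (SD) arm, Table 5 note d states: "The last PK sample (i.e., 24 hours after the end of administration) will occur on Day 2". In the multiple-dose (MAD) arms the profiles after doses 1 and 2 end at redosing. The profile after dose 3 is optional and also ends at 24 h (Table 6 note e).

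SAP 9 fixes the analyte: "Endogenous pGSN + Exogenous pGSN (total) will be referred to as pGSN". SAP 9.1 estimates the PK parameters for pGSN. AUC0-t runs "to the last time point (24 hours) with measurable analyte concentration", and AUC0-inf is "the sum of AUC 0-t plus the ratio of the last measurable plasma concentration to the elimination rate constant". %AUCext is defined ("Percentage of the extrapolated area under the plasma concentration-time curve"), with no limit and no minimum number of terminal points. The baseline-corrected rhu-pGSN analyses in SAP 9.2 (change from pre-dose, and double delta) yield only AUC0-t, AUC0-8 and Cmax, with their dose-normalised forms.

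pGSN is also measured later. The Synopsis asks sites to "redraw procalcitonin, pGSN, and biomarker samples on Day 3 or 4 and Day 7", and Protocol 9.4 lists pGSN in the frozen aliquot. SAP 10.1-10.2 treats these values as pharmacodynamic summaries only.

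**The concern.** Two features of the plan compound each other.

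- **Window.** The terminal slope may rest on three points (8 h, 12 or 16 h, and 24 h). If the half-life is not short against 24 h, much of AUCinf is Clast/k_el, and CL/F and Vz/F inherit that.
- **Analyte.** Endogenous pGSN does not decay to zero. A log-linear slope fitted to drug plus a persistent background is too shallow, so t1/2 and AUC0-inf come out too large and CL/F too small. The background is a larger fraction of the signal at low doses, so linear kinetics would look dose-dependent.

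The only half-life in the text reviewed is 10-16 h, for lung radioactivity in animals (Protocol 4.4.1). That section describes the PK profile as "consistent with that of a relatively stable, high molecular weight protein". At stake is the secondary objective of characterising the PK profile.

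**Working it through.** The documents state no expected half-life or extrapolated share, so there is no planned figure to reproduce.

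**1. Extrapolated share, exogenous pGSN.** For a mono-exponential decline after an IV push, the share of AUCinf beyond the last sample T is 2^(-T/t1/2). The half-lives are assumptions. In the SD arm, Day 3 is about 48 h and Day 4 about 72 h after the dose.

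| t1/2 | T = 24 h | T = 48 h | T = 72 h |
|---|---|---|---|
| 6 h | 6% | 0.4% | <0.1% |
| 8 h | 12.5% | 1.6% | 0.2% |
| 10 h | 19% | 4% | 1% |
| 16 h | 35% | 12.5% | 4% |
| 24 h | 50% | 25% | 12.5% |

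With T = 24 h the share passes 20% once t1/2 exceeds 24 × ln 2 / ln 5 = 10.3 h. A window of two half-lives leaves 2^(-2) = 25%.

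**2. The SAP's rule on total pGSN.** Take C(t) = B + C0·exp(-kt), with constant endogenous level B and peak increment C0. Fit k_el log-linearly to 8, 12 and 24 h, use the log-down trapezoid, and add Clast/k_el.

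Example with B/C0 = 0.5 and true t1/2 10 h, in units of C0:
- Concentrations at 8, 12 and 24 h are 1.074, 0.935 and 0.690, so apparent t1/2 is 25.5 h and k_el is 0.0272 per hour.
- AUC0-24 = 23.85 and Clast/k_el = 0.690/0.0272 = 25.4, so %AUCext = 25.4/49.2 = 51.5%.
- The true exogenous AUCinf is 10/ln 2 = 14.4. Reported AUC0-inf is 3.4 times too large, and CL/F is 0.29 of its true value.

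| B/C0 | true 10 h appears as | true 16 h appears as | true 24 h appears as |
|---|---|---|---|
| 0.25 | 17.9 h (39% extrapolated) | 24.2 h (50%) | 33.7 h (61%) |
| 0.5 | 25.5 h (51.5%) | 32.3 h (60%) | 43.3 h (68%) |
| 1 | 40.6 h (66%) | 48.4 h (71%) | 62.5 h (77%) |

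If B is constant and C0 is proportional to dose, a ratio of 1 at 6 mg/kg implies 0.5 at 12 and 0.25 at 24 mg/kg. A true 16 h would then appear as 48, 32 and 24 h across the dose levels with no real dose effect.

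**3. Later points on total pGSN make it worse.** With B/C0 = 0.5 and true t1/2 16 h, apparent t1/2 goes from 32 h (8, 12, 24 h) to 43 h with a 48 h point and 58 h with a 72 h point.

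**4. Gain from a Day 3/4 point on corrected values (SD arm).** With 8% assay CV, endogenous pGSN 100-200 mg/L, initial rhu-pGSN 110-440 mg/L and random endogenous drift (all assumed), the standard error of k_el shrinks 1.0-1.25 fold at t1/2 12-16 h, 1.15-1.5 fold at 24 h and 1.6-2.2 fold at 48 h. A simulation with no background or drift is more favourable. At t1/2 16 h and 15% CV, the 5-95% range of one subject's estimate narrows from 10.8-31.0 h to 13.5-19.6 h (adding 48 h) or 14.4-18.0 h (adding 72 h). I rely on the cautious figures.

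Corrected late values can fall at or below zero. Take an increment of 110 mg/L, background 150 mg/L, 8% CV and t1/2 16 h. At 48 h the increment is 110/8 = 13.8 mg/L. The SD of the difference is √((0.08×150)² + (0.08×163.8)²) = 17.8 mg/L, so the chance of a value at or below zero is Φ(-13.8/17.8) = 22%.

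**5. MAD arms.** SAP 3 sets the PK baseline as each study day's own pre-dose value. In units of one dose's increment, with d = 2^(-24/t1/2), the Day 3 pre-dose value holds d + d² of drug. The Day 7 value, about 96 h after dose 3, holds d⁴(1 + d + d²). The difference is -0.22, -0.46, -0.64 and -0.66 at t1/2 10, 16, 24 and 48 h: negative, so unusable in a log-linear fit. Day 4 is only about 24 h after dose 3 and does not extend the window.

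The same subtraction also distorts the 24 h profile. On Day 2 at t1/2 16 h (d = 0.354), the corrected values at 8, 12 and 24 h are 0.604, 0.451 and 0.125, an apparent half-life of 6.9 h.

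**The case against.** The strongest points on the other side:

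- **The half-life is unknown here.** The 10-16 h figure is lung radioactivity in animals. An earlier human IV study is described in Protocol 4.4.2, and some adjoining text was not in the copy reviewed, so a plasma value may exist. This stands: the sizes are conditional, and at 6-8 h the exogenous share is small.
- **%AUCext is already calculated and listed per subject.** This stands. Extrapolation would be visible; what is missing is a rule for acting on it.
- **The later samples may not be interchangeable with the PK samples.** PK uses plasma, while the biomarker aliquot is equal parts serum and plasma. The matrix for biomarker pGSN is not stated, and Protocol 4.3 says pGSN can bind fibrin. This stands as a condition on the fix.
- **Placebo correction is weak for the later point.** The double-delta method uses nominal times, Day 3 or 4 has no fixed clock time, and the SD cohort has two placebo subjects. This stands.
- **Stakes are limited.** The parameters are descriptive, and escalation rests on safety through Day 7. This stands.

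Stronger readings are tempting but unsupported. A reader might infer that pGSN data after 24 h are thrown away; the SAP summarises them by visit and lists them with date and time. A reader might infer that many MAD subjects will lack sampling after the last dose; Day 3 sampling is optional but encouraged, and no count is given. A reader might also infer that adding the later values in every arm would cure the problem. Steps 3 and 5 show that it worsens the total-pGSN fit and fails in the MAD arms under the SAP's baseline.

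**Conclusion.** The point holds in a limited form. The endpoints are for rhu-pGSN, but the planned k_el, t1/2, AUC0-inf, CL/F and Vz/F describe total pGSN over 24 h.

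For a plasma half-life of 10-24 h, 19-50% of exogenous AUCinf is extrapolated. On total pGSN, with a constant background at half the peak increment, that becomes 51.5-68%, and a true 10 h reads as about 25 h. These sizes rest on mono-exponential decline, an assumed half-life and an assumed background ratio.

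The analyte is the larger fault. The 24 h window is secondary, and the existing samples can ease it only in the six active SD subjects. This is an inexpensive improvement that should be made; it does not threaten the safety objective.

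**What to change.** In SAP 9.1 and 9.2:

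1. Derive k_el, t1/2, AUC0-inf, CL/F and Vz/F from the pre-dose-corrected rhu-pGSN profile, with placebo correction where sampling times match. Do not add later points to a total-pGSN fit. For MAD Days 2 and 3, use the Day 1 pre-dose value as baseline for k_el; AUC0-inf on those days still carries drug from earlier doses and should be labelled so.
2. In the SD cohort only, add the planned Day 3/4 pGSN value at its actual time as a supportive estimate beside the 24 h-only one. Make this conditional on documented agreement of assay and matrix. State in advance how corrected values at or below zero are handled.
3. Do not extend MAD profiles by subtracting the Day 3 pre-dose value. Any extension after dose 3 should use the Day 1 pre-dose baseline and be labelled exploratory.
4. Flag t1/2 and AUCinf as not reliably estimated when the sampled window covers less than two estimated half-lives, equivalently when %AUCext exceeds about 25%.

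The cost is SAP wording, programming and a check of assay comparability; no visit, blood draw or dosing changes. The main downside is that recovery of endogenous pGSN may distort the later point, which is why the 24 h-only estimate stays alongside.
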